10.0 Sample Size and Eligibility	
10.1 Number of subjects that will be enrolled at UCSF and affiliated institutions:	
150	
10.2 Total number of subjects that will be enrolled at all sites (Help Text updated 9/13):	
150	
10.3 Estimated number of people that you will need to consent and screen here (but not necessaril enroll) to get the needed subjects:	у
300	
10.4 Explain how and why the number of subjects was chosen (Help Text updated 9/13):	
The numbers are based on statistical power analysis and examination of our findings from previous IVC filter retrospective studies done by UCSF interventional radiology. The most recent study showed that one group of filters had 22% penetration and the other had 10% penetration. However, because the numbers in each group were too small, no significant difference in degree of penetration was found. For sample size, we determined that with \sim 75 patients per group and similar differences in incidence or penetration as our preliminary study (25) (22% & 10%) we will see a significant difference at the p = 0.05 level with power 80%. If the difference is a little wider (25% vs. 10%) we will see significance at 50 patients per group. This calculation is using a comparison of proportions test with a z-statistic.	
To make sure this will be feasible, we looked at the total number of IVC filters placed in the previous year at UCSF Mount Zion and UCSF Parnassus. In 2013, 169 IVC filters were placed in patients between the two hospitals. Since this is a standard of care study and no extra time committment will be required, we expect most patients will be consented and agree to be followed in the study. Over a two year proposed study timeline with on average 340 patients receiving IVC filters, we expect to consent about 300 patients in order to get the 100-150 needed to find significant findings. We expect half of the 300 consented patients to be lost to follow up and not return for follow up imaging and retrieval.	
10.5 * Eligible age range(s):	
 □ 0-6 years □ 7-12 years □ 13-17 years ☑ 18+ years 	

1. Patients scheduled for IVC filter placement at UCSF Moffitt, Mount Zion, or Mission Bay Interventional Radiology Service. 2. 18+ 1. Necessity of permanent IVC filter
Necessity of permanent IVC filter
1. Necessity of permanent IVC filter
2. Genetic or physical abnormalities of the inferior vena cava
3. Circumstances that in the opinion of the primary investigator, patient would be a poor candidate either due to complications in medical condition or lack of ability for follow up. (I.E. PI discretion)
10.8 There are inclusion or exclusion criteria based on gender, race or ethnicity:
C Yes ⓒ No
If yes , please explain the nature and rationale for the restrictions:
^{11.0} Drugs and Devices
11.1 * Investigational drugs or biologics will be used OR approved drugs or biologics will be studied under this application:
C Yes O No
11.2 * Investigational medical devices or in vitro diagnostics will be used OR approved medical devices or in vitro diagnostics will be studied under this application:
⊙ Yes C No
11.3 * A Non-Significant Risk (NSR) determination is being requested for an investigational device:
C Yes ⊙ No
11.4 Verification of IND/IDE numbers: If the sponsor's protocol does not list the IND/IDE number, you must submit documentation from the sponsor or FDA identifying the IND/IDE number for this study. Attach this documentation in the Other Study Documents section of the Initial Review Submission Packet.

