After enrollment, the following procedures will be done during the study: Just as with screening, all of these procedures are part of regular IVC filter placement care.

Randomization:

Randomization will occur on the day of procedure or prior clinic visit with IR physician to either the Denali or Option IVC filter. All IR attending physicians on the protocol are familiar with placement of either filter type. Prior to opening study to accrual, 75 sealed security envelopes with the word Denali printed on a card inside and 75 sealed security envelopes with the word Option will be assembled by IR staff not involved in the research. The envelopes will be mixed up and placed in a bag. Computerized randomization programs and tables were considered but we feel the envelopes will work best as there may be limited time after patient is consented and procedure begins. This is especially true as some filters are placed emergently. Previous IR studies have used this randomization technique with great success.

Filter Placement:

Placement of an IVC filter involves the insertion of a plastic tube (catheter) into a vein in the neck. Some numbing medicine (Lidocaine) will be injected in the skin over the vein before the catheter is inserted. Intravenous medications will be given to induce moderate sedation (Fentanyl for analgesic and Versed for moderate sedation). Once the catheter has been placed into the vein, it will be advanced into the IVC. Once in correct position, x-ray contrast material (x-ray dye-Omnipaqe 350) will be injected through the catheter and x-ray pictures taken. A series of x-ray pictures will be obtained of the IVC. These pictures are taken as part of standard of care to determine the position of the renal veins with respect to the IVC. The

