8.0 Scientific Considerations	
☐ Phase I ☐ Phase II ☐ Phase III ☑ Phase IV	
7.2 If this is a clinical trial, check the applicable phase(s) (Help Text updated 9/13):	
would give two curves from time of insertion to time of CT scan showing penetration. The log rank statistic would look at comparisons over time. Finally, we will also do an analysis of struts counting penetration as one or more and use the total number of penetrating struts as a secondary analysis.	
A correlation test will be performed as well as a survival analysis where a failure is penetration. This	
For sample size, we determined that with \sim 75 patients per group and similar differences in incidence or penetration as our preliminary study (25) (22% & 10%) we will see a significant difference at the p = 0.05 level with power 80%. If the difference is a little wider (25% vs. 10%) we will see significance at 50 patients per group. This calculation is using a comparison of proportions test with a z-statistic.	
IVC filter penetration (defined as greater than 3mm) through the IVC wall be the primary complication we will be measuring.	
Statistical and Power Analysis	

|--|

This study has a hypothesis:

If yes, state the hypothesis or hypotheses:

We hypothesize that there is no significant difference in efficacy and complication rate between the Option and the Denali filter.

8.2 * List the specific aims:

- 1) Determine if there is any difference in filter tilt in the vena cava
- 2) Determine if there is any difference in caval penetration
- 3) Determine if there is any difference in physician satisfaction after filter deployment

8.3 Statistical analysis:

Statistical and Power Analysis

IVC filter penetration (defined as greater than 3mm) through the IVC wall be the primary complication we will be measuring.

For sample size, we determined that with \sim 75 patients per group and similar differences in incidence or penetration as our preliminary study (25) (22% & 10%) we will see a significant difference at the p = 0.05level with power 80%. If the difference is a little wider (25% vs. 10%) we will see significance at 50 patients per group. This calculation is using a comparison of proportions test with a z-statistic.

A correlation test will be performed as well as a survival analysis where a failure is penetration. This would give two curves from time of insertion to time of CT scan showing penetration. The log rank statistic would look at comparisons over time.	

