Single blind CT and x-ray imaging analysis will be conducted by a trained radiologist doctor using standard imaging tools and workstations (Agfa PACS V.6). The radiologist will be unaware which patient received which filter type to minimize any potential bias in searching for IVC filter complications. The radiologist will be instructed to look for the following complications of the IVC filter per Society of

Filter penetration as defined by more then 3mm penetration of IVC wall by one or more

- components of the IVC filter
 - o Also look for signs that other organs or spine were penetrated
- Filter tilt as defined by greater than 15 degrees tilt perpendicular to axis of IVC
- Filter migration as defined by more than 1 cm from initial filter location
- Filter thrombus as defined by clot formed in filter mesh
- Filter fracture as defined by breakage of one or more of filter components

Statistics will be compiled and analysis will be performed by statistician using SPSS software.

Statistical and Power Analysis

Interventional Radiation (SIR) guidelines:

IVC filter penetration (defined as greater than 3mm) through the IVC wall be the primary complication we will be measuring.

For sample size, we determined that with \sim 75 patients per group and similar differences in incidence or penetration as our preliminary study (25) (22% & 10%) we will see a significant difference at the p = 0.05 level with power 80%. If the difference is a little wider (25% vs. 10%) we will see significance at 50 patients per group. This calculation is using a comparison of proportions test with a z-statistic.

A correlation test will be performed as well as a survival analysis where a failure is penetration. This would give two curves from time of insertion to time of CT scan showing penetration. The log rank statistic would look at comparisons over time.

Finally, we will also do an analysis of struts counting penetration as one or more and use the total number of penetrating struts as a secondary analysis.	
If you have a procedure table, attach it to the submission with your other study documents.	
14.2 Interviews, questionnaires, and/or surveys will be administered or focus groups will be condu	ıcted:
⊙ Yes C No	
List any standard instruments used for this study:	
Questionnaire given to IR docs after filter placement	
Attach any non-standard instruments at the end of the application.	
14.3 Conduct of study procedures or tests off-site by non-UCSF personnel:	
C Yes O No	

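### With 75 per group the named z-test has about 52% power for 22% vs 10%, not 80%; the 50-per-group fallback for 25% vs 10% has about 51%

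*Combined protocol and SAP*

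**What the plan says.** The same sample-size paragraph appears in Sections 7.1, 8.3, 10.4 and 14.1. It makes three statements:

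- **Main scenario:** for about 75 patients per group, at the rates of the preliminary study, "22% & 10%) we will see a significant difference at the p = 0.05 level with power 80" per cent.
- **Fallback:** "If the difference is a little wider (25% vs. 10%) we will see significance at 50 patients per group". No separate power is attached to this sentence.
- **Method:** "This calculation is using a comparison of proportions test with a z-statistic".

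Allocation is equal: Section 7.1 prepares "75 sealed security envelopes with the word Denali printed on a card inside and 75 sealed security envelopes with the word Option". Enrolment is 150 (10.1 and 10.2). Section 10.4 then describes 100 to 150 patients as the number needed for significant findings. The plan does not say whether the test is one- or two-sided. The relevant aim in 8.2 has no direction: "Determine if there is any difference in caval penetration".

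**The concern.** The paragraph supplies every input to a standard calculation except sidedness, so its result can be checked directly. A 12-point difference around a mean rate of 16% is hard to detect with 75 per group, and 80% looked too high.

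This calculation is the only quantitative reason given for enrolling 150 patients. Section 10.4 also says that the previous retrospective comparison found no significant difference because its groups were too small. If the new size is about half of what is needed, the trial repeats that weakness. The hypothesis in 8.1 makes this worse, because it predicts no significant difference between the filters. An underpowered comparison that misses a real 22% versus 10% difference would then read as support for the hypothesis, and a quoted 80% power would make that reading look credible. The fallback sentence also makes 100 patients in total appear sufficient.

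**Working it through.** **Inputs.** Rates of 22% vs 10% with n = 75 per group, and 25% vs 10% with n = 50 per group (10.4). Significance level 0.05 and target power 80% (10.4). Two-proportion z-test (10.4, 14.1). Allocation 1:1 (7.1). Two-sided is assumed because the aim in 8.2 has no direction; one-sided is shown as well. Every patient counted is treated as evaluable.

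**Power formula (pooled z-test).** With d = p1 − p2 and p̄ = (p1 + p2)/2:

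- SE0 = √[2p̄(1 − p̄)/n], under no difference
- SE1 = √[p1(1 − p1)/n + p2(1 − p2)/n], under the assumed rates
- Power = Φ[(d − 1.960 × SE0)/SE1]

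**Attempt to reproduce the stated 80% (75 per group, 22% vs 10%).** d = 0.12 and p̄ = 0.16.

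- SE0 = √(2 × 0.16 × 0.84/75) = 0.05987
- SE1 = √[(0.22 × 0.78 + 0.10 × 0.90)/75] = 0.05906
- Power = Φ[(0.12 − 1.960 × 0.05987)/0.05906] = Φ(0.045) = **51.8%**

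**Fallback (50 per group, 25% vs 10%).** d = 0.15 and p̄ = 0.175.

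- SE0 = √(2 × 0.175 × 0.825/50) = 0.07599
- SE1 = √[(0.25 × 0.75 + 0.10 × 0.90)/50] = 0.07450
- Power = Φ[(0.15 − 1.960 × 0.07599)/0.07450] = Φ(0.014) = **50.6%**

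**Size needed for 80% power.** n = {1.960√[2p̄(1 − p̄)] + 0.842√[p1(1 − p1) + p2(1 − p2)]}² / d²

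- 22% vs 10%: (1.0162 + 0.4305)²/0.12² = 145.3, so **146 per group**, 146/75 = 1.95 times the stated size
- 25% vs 10%: (1.0532 + 0.4434)²/0.15² = 99.5, so **100 per group**, 100/50 = 2.00 times the stated size
- Check: 150 per group gives 81.2% for 22% vs 10%, and 100 per group gives 80.2% for 25% vs 10%

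**Other versions of the test.**

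| Version | 75/group, 22% vs 10% | 50/group, 25% vs 10% |
|---|---|---|
| Two-sided, pooled | 51.8% | 50.6% |
| Two-sided, unpooled | 52.9% | 52.1% |
| Two-sided, arcsine | 53.1% | 52.3% |
| Two-sided, exact power of the z-test | 53.1% | 53.0% |
| Two-sided, continuity-corrected | 42.8% | 40.0% |
| One-sided 0.05, pooled | 64.2% | 63.1% |
| n per group for 80%, one-sided pooled | 115 | 79 |

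The highest one-sided value for the main scenario is 65.9% (exact). No version reaches 80%.

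**What 75 per group does support (two-sided, pooled).** For 25% vs 10%, power is Φ[(0.15 − 1.960 × 0.06205)/0.06083] = Φ(0.467) = 68%. Solving for the rate that gives 80% power against 10% yields 27.8%.

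**Possible origin (inference only).** Omitting the factor of 2 for two groups gives (1.960 + 0.842)² × p̄(1 − p̄)/d² = 73.3 and 50.4, close to the stated 75 and 50. Alternatively, observed rates exactly equal to the assumed ones just reach significance at these sizes: z = 0.12/0.05987 = 2.00 (p = 0.045) and z = 0.15/0.07599 = 1.97 (p = 0.048). A size chosen in that way has roughly 50% power. The result does not depend on which explanation is right.

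**The case against.** The arithmetic for 75 per group cannot be rescued, but several points narrow the criticism.

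- **The 80% is attached only to 75 per group.** The fallback sentence states no power, and observed rates of exactly 25% and 10% would indeed give p = 0.048. As a planning statement it still fails: it promises significance when the chance, if those are the true rates, is about one half.
- **Sidedness is not stated.** One-sided, the stated sizes are 75/115 = 65% and 50/79 = 63% of the requirement, so the description of them as half holds only for a two-sided test. The 80% fails either way.
- **The z-test is named only for the sample-size calculation.** The listed analyses are a correlation test, a log-rank comparison and a strut count, and no primary test is designated. The log-rank test does not recover the claim. With 75 × (0.22 + 0.10) = 24 expected events and a log hazard ratio of ln(ln 0.78/ln 0.90) = 0.858, the usual events approximation gives Φ(0.858 × √24/2 − 1.960), about 56%.
- **No rule stops the trial at 100.** Enrolment is fixed at 150 and 150 envelopes are prepared. The risk comes only from the fallback sentence and the 100 to 150 figure in 10.4, but both are in the plan.
- **75 evaluable per group is not assured.** Section 10.4 says "We expect half of the 300 consented patients to be lost to follow up and not return for follow up imaging and retrieval". If half of the 150 randomized patients were lost, about 37.5 per group would remain and power would be about 29%. It is also true that 22% was the rate for the Gunther Tulip, which is not a trial device (9.2). Both are separate issues; neither makes the stated 80% correct.

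**Conclusion.** The stated power is wrong. At two-sided 0.05 with all 75 patients per group evaluable, power for 22% vs 10% is about 52%, which is 28 percentage points below the claim; one-sided it is about 64%. The 50-per-group scenario has about 51% power (63% one-sided). Two-sided, the sizes needed for 80% are 146 and 100 per group, about twice those stated. These figures rest on the plan's own rates, 1:1 allocation and the named test. The only added assumption is sidedness, and the conclusion survives either choice. Because this figure is the basis for the trial's size, it must be corrected.

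**What to change.** Replace the sample-size statement in 7.1, 8.3, 10.4 and 14.1 with:

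> With 75 evaluable patients per group, a two-sided 0.05 z-test for two proportions has about 52% power for 22% vs 10% and about 68% for 25% vs 10%. It has 80% power for 10% vs about 28%. Power of 80% would need about 146 evaluable patients per group for 22% vs 10%, or 100 per group for 25% vs 10%.

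Delete the statement that 50 per group is enough and, in 10.4, the statement that 100 to 150 patients are needed.

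The cost is wording and a less favourable stated power; no patients or procedures are added. The correction makes the power statement true but does not raise the power. Keeping 150 is then a choice made on feasibility, and 10.4 already has the figures to say so. At its expected 50% loss, 2 × 146 = 292 evaluable patients would need about 292/0.5 = 584 consented, against about 340 filter placements in the two-year window.

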7.0 Study Design

7.1 * Study design (Help Text updated 9/13):

This is a prospective, randomized trial comparing two FDA-approved inferior vena cava filters, the Denali retrievable IVC filter (Bard Peripheral Vascular Inc., Tempe, AZ) and the Option Elite (Argon Medical, Athens, Texas).

Patients scheduled for IVC filter placement at UCSF Department of Interventional Radiology (IR) will be asked by the IR physician at either UCSF Mt. Zion, Moffitt or the new Mission Bay hospital if they wish to participate in this prospective, randomized study. Recruitment will be conducted by the physicians performing the IR procedures only. No additional recruitment calls, emails, posters or web pages are necessary. All procedures and the randomization to one of the two experimental groups will be carefully explained before obtaining and having participant signed written consent.

Screening:

Screening will be conducted by the IR physician prior to the placement of the IVC filters. Since this is a standard of care study, patients who are recommended for IVC filter placement and are scheduled for the procedure are generally eligible.

The screening procedures are part of routine care before IVC filter placement and would be done even if patients did not join the study.

The study doctor will review the results of most recent routine care imaging scans (CT or MRI) of the abdomen and pelvis. This is done to confirm that the diameter of IVC is no wider than 2.8cm. Both filters are FDA-approved to be placed in an IVC with maximal diameter of 2.8cm.

The study doctor will also review ultrasound of the lower extremity, when available, to confirm that a blood clot was in fact present prior to performing the study. This ensures that patients who present for IVC filter placement are screened properly.

The following screening procedures should be done within 12 days before the IVC filter placement procedure as part of the standard of care.

- · A complete physical exam
- \cdot $\,$ The study doctor will ask about medical history and how well patient is able to do daily activities
- Routine care blood tests (about 2 tablespoons)
 - o This is to ensure that the INR and platelet count of the patient is within the safe limits to perform an invasive procedure.

After Enrollment:

If the screening procedures show that the patient is eligible and consents to take part in the study, IVC filter placement will occur after randomization.

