At follow-up appointment these routine tests per standard of care before IVC filter removal will be performed:

- A physical exam
- · The study doctor will ask about medical history, how well patient is able to do daily activities, and if they are experiencing any possible symptoms related to the IVC filter placement such as abdominal or back pain.
- A rotation CT focused to the site of the filter will be performed as part of routine practice of filter removal. This is done to ensure the filter has not migrated or that the filter has not penetrated through the walls of the IVC such that filter retrieval would be unsafe.
- · IR physician will determine if patient status is stable and safe for IVC filter removal. If not, physician will discuss with primary care doctor if filter needs to remain permanently in patient or if later retrieval should be considered at subsequent follow up visits.
- · IVC filter retrieval will be performed under moderate sedation. This procedure is very similar in nature to the filter placement procedure. The IVC filter is removed via a similar process to the way in which it was placed. X-ray dye (contrast) will be injected around the filter to assure that the filter and the area beneath the filter are free of blood clots and that it is safe to proceed with removal. A catheter-based snare will be used to engage the hook at the end of the filter and the filter will then be enveloped by a removal sheath and removed from the body.

Imaging Analysis:

Single blind CT and x-ray imaging analysis will be conducted by a trained radiologist doctor using standard imaging tools and workstations (Agfa PACS V.6). The radiologist will be unaware which patient received which filter type to minimize any potential bias in searching for IVC filter complications.

The radiologist will be instructed to look for the following complications of the IVC filter per Society of Interventional Radiation (SIR) guidelines:

- Filter penetration as defined by more then 3mm penetration of IVC wall by one or more components of the IVC filter
 - o Also look for signs that other organs or spine were penetrated
- Filter tilt as defined by greater than 15 degrees tilt perpendicular to axis of IVC
- Filter migration as defined by more than 1 cm from initial filter location
- Filter thrombus as defined by clot formed in filter mesh
- Filter fracture as defined by breakage of one or more of filter components

0.1 Hunsthadia (Hala Tautumdatad 0./12).	

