If the screening procedures show that the patient is eligible and consents to take part in the study, IVC filter placement will occur after randomization.

After enrollment, the following procedures will be done during the study: Just as with screening, all of these procedures are part of regular IVC filter placement care.

Randomization:

Randomization will occur on the day of procedure or prior clinic visit with IR physician to either the Denali or Option IVC filter. All IR attending physicians on the protocol are familiar with placement of either filter type. Prior to opening study to accrual, 75 sealed security envelopes with the word Denali printed on a card inside and 75 sealed security envelopes with the word Option will be assembled by IR staff not involved in the research. The envelopes will be mixed up and placed in a bag. Computerized randomization programs and tables were considered but we feel the envelopes will work best as there may be limited time after patient is consented and procedure begins. This is especially true as some filters are placed emergently. Previous IR studies have used this randomization technique with great success.

Filter Placement:

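### 150 is used both as the number randomised and as the number left after half of about 300 patients fail to return; both cannot hold, because randomisation comes before that loss

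*Combined protocol and SAP*

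**What the plan says.** - **Enrolment (10.1, 10.2).** The item "Number of subjects that will be enrolled at UCSF and affiliated institutions" is answered 150, and so is the total for all sites.
- **Screening (10.3).** The item "Estimated number of people that you will need to consent and screen here" is answered 300. Its label adds that these people need not all be enrolled.
- **Justification (10.4).** It says "we expect to consent about 300 patients in order to get the 100-150 needed to find significant findings", and then "We expect half of the 300 consented patients to be lost to follow up and not return for follow up imaging and retrieval". The power statement in the same section counts about 75 patients per group.
- **Randomisation (7.1, repeated in 14.1).** Before accrual opens, staff assemble "75 sealed security envelopes with the word Denali printed on a card inside and 75 sealed security envelopes with the word Option", which makes 150 in all. No provision is made for more.
- **Sequence (7.1, 14.1).** After consent, "IVC filter placement will occur after randomization". Follow-up imaging and retrieval come later.
- **Outcome (7.1, 14.1).** Penetration of more than 3 mm is the primary complication. The imaging is done at the follow-up appointment: "A rotation CT focused to the site of the filter will be performed as part of routine practice of filter removal".

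**The concern.** The form label in 10.3 treats the drop from 300 to 150 as happening before enrolment. Section 10.4 describes the same drop as failure to come back for imaging and retrieval, which can only happen after a filter has been allocated and placed. The figure 150 is therefore doing two jobs, and the plan does not settle how many patients will be randomised or how many are expected in the primary comparison.

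If the trial runs as written, the envelopes are used up at patient 150. At the rate of loss the plan itself expects, roughly half of those patients would have no follow-up CT. A patient who is imaged but not retrieved could still supply the outcome, but the half described in 10.4 return for neither. The hypothesis in section 8 is that there is no significant difference between the filters. A comparison on about 75 patients would probably be non-significant even if the assumed difference were real, and could be misread as support for that hypothesis.

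**Working it through.** **Inputs.** Enrolled 150 (10.1, 10.2). Consented about 300, loss one half, target 100-150 (10.4). Envelopes 75 + 75 (7.1, 14.1). Rates 22% vs 10%, or 25% vs 10%; significance level 0.05; z-test of two proportions (8.3, 10.4). Filters placed in 2013: 169 (10.4). Sidedness is not stated, so both are shown.

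**Step 1: the counts.**
- 10.4: 300 × (1 − 0.5) = 150, so here 150 is the number after loss.
- 10.1, 10.2 and the envelopes: 75 + 75 = 150, so here 150 is the number randomised.
- Reading 1, 150 or 100 evaluable after 50% loss: 150 / 0.5 = 300 randomised, or 100 / 0.5 = 200. Both exceed 150 envelopes.
- Reading 2, 150 randomised with 50% loss: 150 × 0.5 = 75 evaluable, or 37-38 per group if loss is equal by arm (an assumption). This is below even the lower target of 100.

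**Step 2: power at each count.** With n per group, p̄ = (p₁ + p₂)/2, and z = 1.960 two-sided or 1.645 one-sided:

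power = Φ{ [ |p₁ − p₂| − z·√(2p̄(1 − p̄)/n) ] / √( [p₁(1 − p₁) + p₂(1 − p₂)]/n ) }

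The plan's own figure first: n = 75, 22% vs 10%, two-sided. Here p̄ = 0.16, the null standard error is 0.0599 and the alternative standard error is 0.0591. Power = Φ[(0.12 − 1.960 × 0.0599)/0.0591] = Φ(0.045) = 52%. The stated 80% is not reproduced. Under this formula it would need 146 per group two-sided or 115 one-sided.

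At n = 37 the standard errors are 0.0852 and 0.0841, so power = Φ[(0.12 − 1.960 × 0.0852)/0.0841] = Φ(−0.56) = 29%.

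| Randomised | Evaluable per group | 22% vs 10%, two-sided (one-sided) | 25% vs 10%, two-sided (one-sided) |
|---|---|---|---|
| 150, half lost | 37-38 | 29% (41%) | 40% (52-53%) |
| 200, half lost | 50 | 37% (50%) | 51% (63%) |
| 300, half lost | 75 | 52% (64%) | 68% (79%) |

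Exact binomial power of the same test agrees closely: for 22% vs 10% it is 30% two-sided at n = 37 and 53% at n = 75.

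**Step 3: sensitivity, 150 randomised, 22% vs 10%, two-sided.**
- Unequal loss of 40% and 60% (45 and 30 evaluable): 26% or 31%, depending on which arm loses more.
- Lower overall loss of 20% to 40% (60 to 45 per group; an illustrative range): 43% to 34%.

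**Step 4: what is due to attrition.** Loss to follow-up takes two-sided power from about 52% to about 29%. The gap between 52% and the stated 80% is a separate sample-size error.

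**Step 5: feasibility.** 169 × 2 = 338 filters in two years. 300/338 = 89%; 200/338 = 59%.

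**The case against.** The strongest reply is that the authors foresaw the attrition and doubled for it. Section 10.4 consents 300 in order to finish with 100-150. On that view 150 is the evaluable target, and the only slips are the enrolment entries and the envelope count. This is a plausible account of what was meant, but it does not remove the conflict. It says which figures would have to change, and the 75 + 75 envelopes would then stop the trial at half its intended size.

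A second reply is that the 50% applies to patients consented. If some left between consent and allocation, as the label in 10.3 would allow, loss among those randomised would be smaller. It is right that 50% of those randomised is an assumption. It is still the natural one, because failure to return is the only cause that 10.4 gives. The 20-40% range in the working shows that power stays below 45% two-sided for 22% vs 10%.

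Two further points stand. Much of the low power comes from the separate sample-size error and should not be charged to attrition. And the loss bears on outcomes read from follow-up imaging; physician satisfaction is recorded just after placement and is not affected.

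**Conclusion.** The concern holds. The contradiction follows from the plan's own counts and the order of its procedures, and does not depend on any power formula. If 150 are randomised and half do not return, about 75 patients carry the penetration comparison, with about 29% two-sided power (41% one-sided) for 22% vs 10%. If 150 are to be evaluable, 300 must be randomised and the plan provides half the envelopes needed. The power figures rest on three assumptions: 50% loss among those randomised, equal loss by arm, and the plan's assumed penetration rates. This must be fixed, because the numbers to be randomised and analysed are basic design quantities and the plan leaves both open.

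**What to change.** Reconcile 10.1, 10.2, 10.3, 10.4 and the envelope count in 7.1 and 14.1. Give the numbers consented, randomised and expected to be evaluable as three separate figures, and state power, with its sidedness, at the evaluable number. The sponsor then has a choice:

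- **Keep 150 randomised.** Restate the evaluable number as about 75 (37-38 per group), with about 29% two-sided power for 22% vs 10%, and correct the 100-150 target in 10.4. The cost is text only, plus a less favourable stated figure. It removes the contradiction but leaves a weak primary comparison.
- **Randomise about 300** (or 200 if 100 evaluable is the target). Change 10.1 and 10.2 and prepare 150 (or 100) envelopes per arm. For 300, this doubles stated enrolment and needs an amendment and 150 more envelopes. It requires about 89% of the roughly 338 filters expected over two years (59% for 200), after the exclusions. That is close to the plan's own expectation of consenting 300 of 340 (88%). The 169 filters counted for 2013 come from Mount Zion and Parnassus; the plan does not say whether Mission Bay adds to that volume. The text should also say that 300 randomised restores 75 evaluable per group but not 80% power.
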